Multi-Center Evaluation of Clinical Outcomes of Pulse Widths <500 μ sec and >1000 μ sec During a Temporary Spinal Cord Stimulation Trial

Title: Multi-Center Evaluation of Clinical Outcomes of Pulse Widths <500 μ sec and >1000 μ sec During a Temporary Spinal Cord Stimulation Trial

Protocol Number: TBD

Device: Nuvectra® Algovita® Spinal Cord Stimulation System

Sponsor: The Ohio Pain Clinic
[name]
[name]

Sponsor Contact: [name]
[name]
[name]
[contact]

Study Sites: TBD

Medical Monitor: [name]
Ohio Pain Clinic
[name]
[name]

Date of Protocol: TBD

Confidentiality Statement

The confidential information in this document is provided to you as an investigator or consultant for review by you, your staff, and the applicable Institutional Review Board. Your acceptance of this document constitutes agreement that you will not disclose the information contained herein to others without written authorization from .

Protocol Synopsis

Sponsor Contact Information Ohio Pain Clinic
[name]
[name]
[name]

Study Purpose The purpose of this study is to evaluate the effect of pulse widths <500 μ sec and >1000 μ sec on clinical outcomes during a temporary SCS trial.

Study Design and Scope The proposed study is a prospective, multi-center, two-arm, randomized, crossover design to be conducted at up to 10 sites. The study will enroll up to 100 subjects in order to include up to 10 subjects in the study per site. Subjects selected to participate in the trial have back and/or leg pain, have been evaluated as a candidate for SCS and have agreed to undergo a temporary SCS trial using the Algovita® system with percutaneous leads. Each subject will be followed during the trial period of approximately 7+-2 days. The study will end when the last subject has completed the trial period and exited. The expected enrollment period for this study is approximately six months. After exit from the clinical study, subjects will continue to be followed by their physician per usual care. All device and procedure-related AEs will be collected and reported per the study protocol.

Primary Effectiveness Objective Compare the change in the patient defined pain coverage map from baseline to the end of the 7+-2 day trial.

Secondary Effectiveness Objectives Secondary measures of therapy effectiveness will include:

- Compare the change from baseline of pain scores between the two study arms. Pain scores are obtained using the Numeric Rating Score (NRS) administered at baseline and after completion of each arm of the study.
- Paresthesia distribution: At end of each arm, subjects will be asked to complete a diagram that shows distribution of paresthesia.
- At the end of the trial period, subjects will be asked to select their favorite program.
- At the end of the trial period, subjects will be asked to rate the quality of the pain relief achieved during the trial (from either arm) using the following scale; *Excellent, Very Good, Good, Fair or Poor*.
- At the end of the trial period, subjects will be asked to rate their overall satisfaction with the pain relief achieved during the trial (from either arm) using the following scale: *Very Satisfied, Satisfied, Neither Satisfied nor Unsatisfied, Unsatisfied, or Very Unsatisfied*.

Secondary Safety Objectives Secondary measures of therapy safety will include:

- Rate of device-related and/or procedure-related AEs from the Trial procedure through study completion.

Study Procedures After the subject has consented to the study, he or she will be enrolled in the clinical study and undergo a baseline evaluation. The patient will then be randomly assigned to arm one (pulse width <500 μ sec) or arm two (pulse width >1000 μ sec) and undergo an Algovita® trial procedures. Following the trial procedure, the subject's EPG will be set to the appropriate pulse width, based on the arm assigned, and then programmed to achieve optimal pain relief. For the next three days, the subject will evaluate pain relief generated by the 1st assigned program (arms).

After 3 days, the patient will visit the Ohio Pain Clinic for data collection and then reprogramming of the EPG for the next arm. For the next three days, the subject will evaluate the SCS therapy generated by the 2nd assigned program and then return to the clinic for data collection, removal of the leads and exit from the study. After the subject is exited from the study, he or she will be followed by the Ohio Pain Clinic per usual care. The data collection requirements are listed below.

Enrollment:

- Informed consent signed
- Confirmation of study eligibility

Baseline evaluation:

- Record pain ratings and pain map
- Relevant medical history
- Physical examination
- Brief Pain Inventory
- Demographics

After the lead implantation:

- Implant procedure
- Document SCS products & lead configuration, electrode position and programmed parameters

4 and 7 day (+/- 2) Post-Implantation:

- Record pain map data
- Record pain rating for current arm
- Record paresthesia and pain map for current arm
- Document AEs
- Program subject with next arm parameters and document

[figure not shown]
Study Exit

- Record pain map data
- Record pain rating for current arm
- Record paresthesia and pain map for current arm
- Record program preference
- Record satisfaction and pain relief from each program
- Document study exit reason & AEs

TIME AND EVENTS SCHEDULE

Assessments and Data Collection	Enrollment	Baseline	After Implant	Follow-up Visits	Study Exit
• Eligibility confirmation	✓				
• Medical history	✓				
• Physical exam					
• Informed consent	✓				
• Record demographics		✓			
• Brief Pain Inventory		✓			
• Record pain map		✓			
• Implant and system information			✓		
• Record paresthesia and pain map for current arm	✓		✓	✓	✓
• Record pain rating for current arm	✓	✓	✓	✓	✓
• Document any AEs		✓	✓	✓	✓
• Record subject program preference					✓
• Record subject satisfaction and pain relief from each program					✓
• Document study exit reason & any AEs					✓

FLOWCHART

PROTOCOL HISTORY OF CHANGE
TBD

Original issue

Table of Contents

Page	
Protocol Title.....	i
Protocol Synopsis.....	ii
Protocol History of Change/ Summary of Bibliography Studies	vi
List of Abbreviations and Definitions	x
1.0 INTRODUCTION	8
2.0 OBJECTIVES	10
2.1 Primary Objective.....	10
2.2 Secondary Objectives	10
3.0 REGULATORY CLASSIFICATION	11
4.0 DEVICE.....	11
4.1 ALGOVITA® SPINAL CORD STIMULATION SYSTEM.....	11
5.0 STUDY DESIGN.....	12
5.1 OVERVIEW OF DATA COLLECTION AT STUDY VISITS	12
6.0 ENDPOINTS	13
6.1 PRIMARY EFFECTIVENESS ENDPOINT.....	13
6.2 SECONDARY ENDPOINTS.....	13
7.0 MINIMIZATION OF BIAS.....	14
8.0 INVESTIGATORS	15
8.1 INVESTIGATOR SELECTION AND RESPONSIBILITIES	15
9.0 STUDY POPULATION	16
9.1 Inclusion Criteria.....	16
9.2 Exclusion Criteria	16
9.3 Sample Size	16
10.0 Methods and Procedure.....	17
10.1 DATA COLLECTION REQUIREMENTS.....	17
10.1.1 Subject Screening Procedure.....	17
10.1.2 Informed Consent	17
10.1.3 BASELINE VISIT	18
10.1.4 IMPLANT	18
10.1.5 FOLLOW-UP VISITS.....	18
10.1.6 STUDY EXIT.....	18
11.0 ADVERSE EVENT REPORTING.....	20
11.1 ADVERSE EVENTS.....	20
11.2 ANTICIPATED ADVERSE DEVICE EFFECTS	20
11.3 UNANTICIPATED ADVERSE DEVICE EFFECTS.....	21
12.0 STATISTICS	22
12.1 Study Population.....	22
12.2 Safety Analysis	22

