2.0 OBJECTIVES

2.1 Primary Objective

To evaluate the effect of conventional pulse widths <500 μ sec and pulse widths >1000 μ sec on clinical outcomes during temporary trial as measured by patient defined pain maps.

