2.2 Secondary Objectives

Secondary measures of therapy effectiveness will include:

1. To evaluate the effect of conventional pulse widths <500 μ sec and pulse widths >1000 μ sec on clinical outcomes during temporary trial as measured by the percent reduction in targeted pain compared to baseline using the NRS at the end of the trial period.
2. At end of each arm, subjects will be asked to complete a diagram that shows distribution of paresthesia.
3. At the end of the trial period, subjects will be asked to select their favorite program.
4. At the end of the trial period, subjects will be asked to rate the quality of the pain relief achieved during the trial (from either arm) using the following scale; *Excellent, Very Good, Good, Fair or Poor*
5. At the end of the trial period, subjects will be asked to rate their overall satisfaction with the pain relief achieved during the trial (from either arm) using the following scale; *Very Satisfied, Satisfied, Neither Satisfied nor Unsatisfied, Unsatisfied or Very Unsatisfied*
6. Number of patients who achieved $\geq 50\%$ pain relief during the trial (from either arm)
7. Rate of device-related and/or procedure-related AEs from SCS implant through study completion or study exit.

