5.0 ENDPOINTS

The endpoints of the study are focused on collecting data to determine clinical outcomes of Pulse Widths $>1000\mu\text{sec}$ compared to Pulse Widths $<500\mu\text{sec}$ during an SCS trial. Safety data will also be collected at all visits. Data will be collected using:

- Patient generated Pain Maps
- The NRS to assess pain levels
- Questionnaires to assess pain coverage, program preference, overall satisfaction of the trial and AEs

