5.1 PRIMARY EFFECTIVENESS ENDPOINT

The primary effectiveness endpoint is defined as the percent reduction from baseline in targeted patient generated pain map coverage between the two arms.

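### The NRS endpoint has two conflicting time points, and no objective or endpoint sentence ties the primary pain-map endpoint to the end of each arm

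*Combined protocol and SAP*

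**What the plan says.** All references are to the combined protocol and SAP.

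- **Design.** The study is a two-arm randomized crossover. Under Study Procedures in the synopsis, data are taken at a clinic visit when the first arm ends, before the generator is set for the other arm. In the second stretch, "the subject will evaluate the SCS therapy generated by the 2nd assigned program and then return to the clinic for data collection"; the leads then come out and the subject exits.
- **Primary pain map.** The synopsis objective is "Compare the change in the patient defined pain coverage map from baseline to the end of the 7+-2 day trial". Section 2.1 evaluates the two pulse-width ranges "on clinical outcomes during temporary trial as measured by patient defined pain maps". Section 5.0 opens with "The endpoints of the study are focused on collecting data to determine clinical outcomes of Pulse Widths" in the longer range against the shorter. Section 5.1 reads: "The primary effectiveness endpoint is defined as the percent reduction from baseline in targeted patient generated pain map coverage between the two arms".
- **NRS.** The synopsis compares change from baseline between the arms, with scores "administered at baseline and after completion of each arm of the study". Sections 2.2 and 5.2 both define the measure as "percent reduction in targeted pain compared to baseline using the NRS at the end of the trial period".
- **Records.** Sections 9.1.5 and 9.1.6, and the synopsis visit lists, call for the map and the pain rating of the current arm at the day 4 and day 7 visits and at exit.
- **Analysis.** Section 11 consists of a population paragraph (11.1) and a safety analysis (11.2). The only test named for continuous variables is a t-test of the two treatment groups, in 11.2. It is not stated to be paired.

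**The concern.** A crossover earns its efficiency by comparing each subject's response under one treatment with the same subject's response under the other. That needs an endpoint value from the end of each arm. For the NRS, the text supports both that definition and one that takes a single value at the end of the trial. For the primary endpoint, one sentence supplies a time point without arms and another supplies arms without a time point.

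If the end-of-trial wording is followed, the first-arm values drop out and the within-subject comparison goes with them. Because no effectiveness analysis is written down, the choice could also be made after the data have been seen.

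**Working it through.** **Step 1: set the definitions side by side.**

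| Place | Outcome | Time point | Comparison named |
|---|---|---|---|
| Synopsis, primary objective | Pain map | End of the 7±2 day trial | None |
| 2.1 | Pain map | None beyond the temporary trial | Two pulse-width ranges |
| 5.1 | Pain map | None | Between the two arms |
| Synopsis, secondary objectives | NRS | After each arm | Between the two arms |
| 2.2 and 5.2 | NRS | End of the trial period | Two pulse-width ranges |

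The two NRS phrases are not loose synonyms. In the list in 2.2, the NRS item uses the end of the trial period and the next item, the paresthesia diagram, uses the end of each arm. The protocol uses the phrases for different moments and gives the NRS both. For the pain map there is no direct contradiction, but no objective or endpoint sentence joins the time point to the arms.

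**Step 2: what the end-of-trial wording delivers.** At that point each completer is on the second program. There is one value per subject, and treatment can be separated only by comparing the two sequence groups.

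**Step 3: illustrate the cost.** The plan has no figure to reproduce. Section 8.3 gives a cap of 100 subjects and no power, effect size, standard deviation or correlation. Assume N subjects split equally between sequences, a common variance V, and a correlation r between a subject's two values on the analysed scale.

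- Second-period comparison: V/(N/2) + V/(N/2) = 4V/N.
- Within-subject comparison: each subject's difference has variance 2V(1-r), so the period-adjusted estimate has variance 2V(1-r)/N.
- Ratio: (4V/N) / (2V(1-r)/N) = 2/(1-r).

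| Assumed r | Ratio 2/(1-r) | Subjects in a within-subject analysis giving the same precision as second-period data on 100: 100(1-r)/2 |
|---|---|---|
| 0 | 2.0 | 50 |
| 0.3 | 2.9 | 35 |
| 0.5 | 4.0 | 25 |
| 0.7 | 6.7 | 15 |

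The ratio is at least 2 for any r of 0 or more. A negative r would bring it below 2, but it exceeds 1 for every r above -1.

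**Step 4: bias.** A period effect common to both sequences cancels in both estimates. If the carryover from the two programs differs by L, the second-period comparison is biased by L. In the within-subject estimate the carryover enters only the second value of each pair, and averaging over the two sequences leaves L/2. A simulation with L = 0.2 and a period effect of 0.5 gave biases of 0.201 and 0.102.

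**Step 5: check whether the schedules settle the matter.** As they read, they do not. The Time and Events Schedule and the table in 4.1 tick the plain pain-map row at baseline only and use the current-arm row at follow-up and exit. Table 6-1 in 9.1.1 ticks the plain row at baseline, follow-up and exit and leaves the current-arm row blank. Table 6-1 shows no baseline pain rating, although 9.1.3 collects the NRS then. Section 9.1.5 lists programming of the next arm for both follow-up visits, while the synopsis describes two arms with one change between them.

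**The case against.** The strongest reply is that the intention is clear. The design is a crossover, 5.1 compares the arms, and the current arm's map and rating are recorded at every post-implant visit. The synopsis places data collection before reprogramming and lists it ahead of lead removal. The synopsis objective may be describing the observation window and not one analysis visit. The NRS sentence in the synopsis says when scores are taken, and 2.2 and 5.2 still set out to evaluate the pulse-width ranges. On this view nothing would be lost, and the variance ratios size a reading that few analysts would choose.

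Much of this stands. The per-arm reading is the natural one and its data are planned. The ratios rest on assumed correlations, and none is derived for the percent scale that 5.1 uses. The schedule differences are secondary: tick marks can shift when a table is converted to text, and a blank baseline cell in a row for the current arm is weak evidence, since no arm is running at baseline.

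The reply does not remove the NRS conflict, which is in the wording of the objective and endpoint themselves. Nor does it supply the missing link for the primary endpoint. Scheduling a record does not say which record enters the analysis, and Section 11 does not say so either.

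**Conclusion.** The point holds as an inconsistency in endpoint definition that should be corrected. The NRS has two conflicting time points. The primary endpoint has a between-arm comparison in 5.1 and an end-of-trial time point in the synopsis, and no objective or endpoint sentence connects them. Following the end-of-trial wording would leave a between-sequence comparison with 2/(1-r) times the variance of the within-subject one: 2.0 at r = 0 and 4.0 at r = 0.5. This assumes equal sequences and equal variances, with r not given in the documents. It applies only if that wording is followed.

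Three stronger readings are tempting and are not supported:

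- A reader might infer that no between-arm comparison is stated for the primary endpoint. Section 5.1 states one.
- A reader might infer that first-arm maps or ratings would not be collected. Sections 9.1.5 and 9.1.6 schedule them.
- A reader might infer a known loss of power. The plan contains no power calculation, so only the illustrative ratio can be given.

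**What to change.** 1. In the synopsis, 2.1 and 5.1, define the primary endpoint as percent reduction from baseline in the pain map recorded at the end of each arm (before reprogramming for the first arm, before lead removal for the second), compared within subject, >1000 versus <500 µsec.
2. In 2.2 and 5.2, move the NRS time point to the end of each arm, to match the synopsis. Use the percent scale throughout; the synopsis currently speaks of change.
3. In Section 11, add an effectiveness analysis for both endpoints: a period-adjusted paired comparison, or a mixed model with treatment and period fixed and subject random. Report the treatment difference with a 95% confidence interval. State that the two-group t-test in 11.2 does not apply to these endpoints.
4. Reconcile the pain-map and pain-rating rows of the Time and Events Schedule, the table in 4.1 and Table 6-1. Reconcile the next-arm programming item in 9.1.5 with the two-arm sequence in the synopsis.

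The cost is wording, one analysis paragraph and a schedule clean-up, with no added visit or procedure. The small downside is that the within-subject estimate still carries half of any unequal carryover, and no washout is described. A first-period comparison could be reported alongside it as a check.

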The Algovita® SCS System is similar in design and performance to newer SCS systems from other medical device companies. The FDA approved Algovita® system has many advanced features including the ability to better control the shape of the electrical pulse. One such feature is a longer pulse width range than the other systems on the market. Pulse width determines how long an electrical pulse is activated. A longer pulse width is not associated with any safety concerns as determined by the FDA. The intent and justification for this study is to understand if a longer pulse width provides better outcomes to patients.

Although the effects of pulse width are mentioned in many SCS investigations, it has been the primary focus of very few studies. Several decades ago, research was conducted into the technical aspects of SCS, including PW. In a study of SCS, Jobling showed that different patients required widely varying amplitudes of stimulation and concluded that 200 μ sec was the optimum pulse duration, because it was the most energy- efficient^{vi}. In 1980, Davis and Gray concurred that 200 μ sec was the preferred PW to deliver adequate amplitude while conserving energy^{vii}. Some published reports suggested that there was therapeutic value to having higher parameter ranges than were available on previous primary cell IPGs. In addition, longer PWs have been anecdotally described as achieving better pain-paresthesia overlap and comfort for the patient, thus potentially more effective at relieving pain^{viii}.

The introduction and widespread adoption of rechargeable IPGs for SCS has diminished the importance of energy efficient programming to prolong time between revision surgeries and resulted in longer pulse width settings in these systems. Gould and Bradley reported in a retrospective analysis of patient-preferred programs that over 50% of the programs used PWs in excess of 450 μ s^{ix}. Yearwood et al. showed that 10/19 patients had greater coverage, and 8/19 patients displayed “caudal shift” of paresthesia coverage with increased PW^x. A mathematical model of electrical field and neural activation in SCS has shown good agreement with clinical data that a longer PW is associated with increased paresthesia coverage and a shift of the paresthesia coverage caudally^{xi}.

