9.1.4 IMPLANT

The implant trial procedure will be performed within 28 calendar days following the Baseline Visit. Appropriately trained field staff will assist as necessary with the Algovita® Trial Lead implant. The recommended placement for the device will be determined by the physician and documented on the CRF. Information regarding the devices used, location, and procedure data will be collected on an Implant CRF. A Nuvectra® representative may be present during the implant procedure and may assist in the programming of the Algovita® system at the Investigator's direction.

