9.1.5 FOLLOW-UP VISITS

Follow-up visits will occur at day 4 and 7 (+/-2) post-implantation. Data collected at these visits will be recorded on case forms (CRFs) and will include:

- Record paresthesia and pain map for current arm
- Record pain rating for current arm
- Document AEs
- Program subject with next arm parameters and document

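### An optimisation goal and possible manufacturer help with programming are stated only for the first program, and nothing controls programming across the two crossover periods

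*Combined protocol and SAP*

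**What the plan says.** The design is a "two-arm, randomized, crossover design" (Protocol Synopsis, Study Design and Scope). Under Study Procedures in the synopsis, subjects are randomised before the trial procedure. Afterwards the subject's "EPG will be set to the appropriate pulse width, based on the arm assigned, and then programmed to achieve optimal pain relief".

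The change to the second program is described more briefly. The synopsis says: "After 3 days, the patient will visit the Ohio Pain Clinic for data collection and then reprogramming of the EPG for the next arm". Section 9.1.5 has one line in its list of visit data: "Program subject with next arm parameters and document". The synopsis list for the day 4 and day 7 visits has the same line.

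On who programs, Section 9.1.4 says that a Nuvectra "representative may be present during the implant procedure and may assist in the programming of the Algovita® system at the Investigator's direction". No corresponding statement is made for the follow-up visit.

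Section 6.0 (Minimization of Bias) lists eligibility screening, collection of demographics, standardised training and adherence to the investigational plan. It has no programming routine and no rule on who programs. No section mentions blinding. Section 11 gives no effectiveness analysis with a period or sequence term; its t-test and chi-square comparison stands under Safety Analysis.

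**The concern.** In a crossover, the two periods should differ only in the treatment given. Read literally, the text gives the first program a target and possible expert help, and gives the second neither. Pain maps, NRS scores, paresthesia overlap and program preference could all respond to how well a program was tuned as well as to its pulse width.

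Two routes need to be kept apart. One is a period effect: the first program is tuned better, whichever arm it is. The other is an arm effect: someone who knows the pulse width puts more work into one arm. Randomised order protects against the first under certain conditions. It does not protect against the second.

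**Working it through.** **Inputs.** The plan states no figure on this point, so there is none to reproduce. It gives no SD, effect size, alpha, power, allocation ratio or randomisation method. The following are therefore assumptions, in NRS points:
- d = advantage of the first program, equal in both arms: 1 and 1.5.
- SD of the within-subject difference (long minus short pulse width): 2, so its variance is 4.
- e = advantage from extra effort on the long pulse width: 0.3.
- p = share of subjects who receive the long pulse width first.

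The sample sizes of 50 and 100 come from Section 4.0 (enrol up to 100 to assure at least 50).

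**Route 1: better tuning in period 1, equal in both arms.** The difference shifts by +d in subjects with long first and by −d in subjects with short first.
- Mean bias, unadjusted: p·d − (1 − p)·d = (2p − 1)·d. At p = 0.5 this is 0. At p = 0.6 it is 0.2·d, which is 0.2 points at d = 1 and 0.3 at d = 1.5.
- Mean bias with a period term: (d − d)/2 = 0 at any split.
- Under simple randomisation, the absolute value of 2p − 1 averages about 0.11 at n = 50 and 0.08 at n = 100 (95th percentile 0.28 and 0.20). At d = 1 the shift from chance imbalance is therefore about 0.11 or 0.08 points on average.
- Variance used by a paired analysis without a period term, equal sequences: 4 + d². Relative to 4, this is (4 + 1)/4 = 1.25 at d = 1 and (4 + 2.25)/4 = 1.56 at d = 1.5.
- Sensitivity: the inflation is d²/SD². Doubling the assumed SD divides it by four, to 1/16 = 6% and 2.25/16 = 14%.

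**Route 2: extra effort on the long pulse width.**
- Confined to period 1: the difference shifts by e in subjects with long first and by 0 in the others. With equal sequences the bias is e/2, and a period term leaves it at (e + 0)/2 = e/2. For e = 0.3 this is 0.15 points.
- Present in both periods: every subject's difference shifts by e, so the bias is e = 0.3 points.
- Neither balanced sequences nor a period term removes this bias.

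**The case against.** The strongest reply is that silence is not a rule. A protocol that describes programming once and later calls for reprogramming would ordinarily be read as repeating the same step at the other pulse width. Section 9.1.5 is a data-collection list, not a programming instruction, and the flowcharts are not shown. This stands: a reader might infer that the second program is not to be optimised, but the documents do not say so.

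A reader might also infer that first-period optimisation by itself biases the pulse-width comparison. It does not if sequences are balanced or period is modelled; what it then costs, without a period term, is precision. The protocol states neither safeguard.

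A third tempting inference is that the manufacturer's representative would favour the long pulse width. The Introduction does present it as a distinguishing feature ("One such feature is a longer pulse width range than the other systems on the market"). But both arms use the same commercial system, the sponsor is the clinic, and the help is optional, under the Investigator's direction and mentioned only at implant. The documents show an opportunity for unequal effort, not a motive acted upon. Help confined to implant also supports e/2, not e.

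Nor can it be said that no form records programming effort, because the draft CRFs are not shown. Programmed parameters are to be documented for both programs. Settings alone, however, do not show who programmed or for how long.

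The training and plan-adherence items in Section 6.0 do not answer the point. Adherence cannot equalise programming when the plan contains no programming routine.

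**Conclusion.** The point holds as a gap in control, not as a demonstrated bias. The protocol states a programming goal and possible manufacturer help for the first program only, is silent on both for the second, and leaves programming by someone who knows the arm uncontrolled.

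The period route costs precision (25% to 56% more variance under the stated assumptions) and biases the mean only if sequences are unequal and period is ignored, or if optimisation helps one pulse width more than the other. The arm route would bias the estimate by 0.15 to 0.3 points for an assumed e of 0.3. These figures are illustrative. They are in NRS points, a secondary endpoint; the effect on the primary pain-map endpoint cannot be sized from the documents. This is a cheap improvement, best made before enrolment because programming effort is hard to reconstruct afterwards.

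**What to change.** - Reconcile the synopsis (Study Procedures) with Sections 9.1.4 and 9.1.5 so that the same programming goal and the same written routine apply to both programs.
- Add to Section 6.0 that the same programmer sets both of a subject's programs, and that the manufacturer's representative assists with both or with neither.
- Record on the CRF, for each program, who programmed it and how long it took, beside the parameters already documented. Tabulate these by pulse width and by period.
- Include a period term in the within-subject comparison of the two pulse widths.

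No stimulation setting, time limit or clinical rule is proposed. The cost is some protocol wording, a few CRF fields and a scheduling constraint on who programs.

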10.2 ANTICIPATED ADVERSE DEVICE EFFECTS

The following ANTICIPATED EVENTS have been identified as possible complications of implanting neurostimulator leads.

- Infection at implant site
- Pain at implant site
- Bleeding
- Bruising
- Device failure
 - Unintended stimulation
 - Increased stimulation
 - Decreased stimulation
 - Lead breakage/migration
 - Battery depletion
 - Erosion of device
 - General device failure

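### The two programs run back to back and the scoring window for each arm is undefined, so residual effect of the first program can enter the second score and shrink the pulse-width contrast

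*Combined protocol and SAP*

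**What the plan says.** **Sequence of events (Synopsis, Study Procedures).** "Following the trial procedure, the subject's EPG will be set to the appropriate pulse width, based on the arm assigned". The subject evaluates that program for three days. At the visit that follows, "the patient will visit the Ohio Pain Clinic for data collection and then reprogramming of the EPG for the next arm". Then "For the next three days, the subject will evaluate the SCS therapy generated by the 2nd assigned program", after which data are collected, the leads are removed and the subject exits.

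**Scoring.** Sections 9.1.5 and 9.1.6 both ask sites to "Record pain rating for current arm" and to record a paresthesia and pain map on the same basis. Neither says what stretch of time the subject should have in mind. The Synopsis adds, under the secondary effectiveness objectives, "Pain scores are obtained using the Numeric Rating Score (NRS) administered at baseline and after completion of each arm of the study".

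**Timing.** Section 9.1.5: "Follow-up visits will occur at day 4 and 7 (+/-2) post-implantation". Section 9.1.4 lets the baseline precede insertion by up to 28 days.

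**Implant-site pain.** Section 10.2 lists "Pain at implant site" among the anticipated events.

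**Schedule tables.** The tables in the Synopsis and Section 4.1 tick a current-arm rating and map in the After Implant column. The table in Section 9.1.1 does not.

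**What is absent.** No washout, discarded early interval, post-insertion baseline, sequence ratio or period term appears. Section 6.0, on bias, does not mention order or carryover. The only test named for continuous variables is a two-group t-test, in Section 11.2 under safety.

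**The concern.** A crossover compares the programs fairly only if the second score reflects the second program. Here the switch is made in one visit, and the Synopsis has the subject evaluate each program over three days. A subject asked to rate the current arm may well summarise all three days, including early hours when relief from the first program might persist. That would pull the two arms together on the one question the study asks, and the loss would run towards a finding of no difference. It would apply to the primary pain-map endpoint (Section 5.1) as well as to the NRS.

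A first-period summary would likewise include the day of insertion and early recovery, set against a baseline taken before insertion. In a subject with back pain, implant-site pain could be drawn on or near the target area.

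**Working it through.** The protocol gives no power calculation (Section 8.3 states only a cap of 100), so there is no figure of its own to reproduce. Every magnitude below is an assumption.

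**1. Carryover.** Let A and B be the true effects of the two programs, and let the same fraction c of the first program's effect be present in the second score.

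- *Residual displaces the second effect.* Sequence AB gives A - [(1-c)B + cA] = (1-c)(A-B). Sequence BA gives [(1-c)A + cB] - B = (1-c)(A-B).
- *Residual adds to the second effect.* AB gives A - (B + cA). BA gives (A + cB) - B. Their average is (1 - c/2)(A-B).

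Averaging the two sequences is what a period term does, and the factor survives it. Randomised order therefore does not remove it either.

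For a comparison with 80% power at c = 0 (two-sided 5%, normal approximation), power = Φ(2.80 × factor - 1.96):

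| c | Retained, additive | Retained, displacing | Power, additive | Power, displacing |
|---|---|---|---|---|
| 0.10 | 95% | 90% | 76% | 71% |
| 0.25 | 87.5% | 75% | 69% | 56% |
| 0.50 | 75% | 50% | 56% | 29% |

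If the score averages 72 hours and the residual lasts h hours, c = h/72. Then 12 h gives c = 0.167 (loss 8% to 17%) and 24 h gives c = 0.333 (loss 17% to 33%).

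**2. Implant-site pain as a period effect.** Let it raise first-period scores by P whichever arm comes first. The A - B difference gains +P in sequence AB and -P in BA.

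- Bias without a period term = P × (n_AB - n_BA)/N, which is zero with equal sequences.
- Under simple 1:1 randomisation the mean absolute imbalance is 11% of N at N = 50 and 8% at N = 100 (95th percentiles 28% and 20%).
- If insertion adds 2 NRS points for 24 of 72 hours, P = 2 × 24/72 = 0.67. Typical bias is 0.67 × 0.08 = 0.05 to 0.67 × 0.11 = 0.07 points. A 60/40 split gives 0.67 × 0.20 = 0.13.
- Without a period term, the variance of the paired difference is multiplied by 1 + P²/SD². At P = 1 this is 1 + 1/4 = 1.25 for SD 2 and 1 + 1/9 = 1.11 for SD 3.

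A period term removes both the imbalance bias and the added variance.

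**3. What a last-24-hours window achieves.** It clears the residual when h ≤ L - 24, where L is the period length in hours. At L = 72 that covers residuals of up to 48 h. The visit windows do not guarantee L = 72. Counting insertion as day 0, period 1 can last 4 - 2 = 2 to 4 + 2 = 6 days. If only the second visit moves, period 2 lasts 5 - 4 = 1 to 9 - 4 = 5 days. If both move independently, the range is 5 - 6 = -1 to 9 - 2 = 7 days, so the windows overlap. In a one-day period the last 24 hours is the whole period and the window removes nothing; 12 h of residual would then be c = 12/24 = 0.50.

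**The case against.** The strongest reply is that a three-day summary is nowhere prescribed. The NRS is given on completion of each arm, and a rating of present pain at that moment fits the text. On that reading a residual of a day or less, after a three-day period, has no effect. The draft case report forms, where look-back wording would normally sit, are in an appendix that is not available here. This stands in part: the whole-period summary is an inference, and the defect is that the window is unstated.

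It is also fair that a temporary trial typically lasts 5 to 10 days (Section 1.0), which leaves little room for a washout. The Synopsis already puts data collection before reprogramming and lead removal. The endpoints refer to targeted pain, which points away from the incision, although no instruction tells subjects to leave it off the map.

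A reader might infer four stronger things that the documents do not support:

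- *That carryover is present and of known size.* They give no size or duration, and the larger losses assume full displacement. If the programs differed in the fraction that persists, the contrast need not simply shrink.
- *That implant-site pain favours one pulse width.* It falls on whichever arm comes first, and randomised order balances it in expectation.
- *That a subject whose first-program relief is understated is lost from the count reaching 50% relief.* Sections 2.2 and 5.2 count relief from either arm, so the second program can still qualify the subject.
- *That each arm is rated only once.* Two of the three schedule tables also tick a rating after implant.

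**Conclusion.** The point holds as an unaddressed risk. With no gap and no scoring window, first-program effect can enter the second score, and nothing in the design or analysis would remove it. Its size is unknown. Under proportional carryover, the same fraction c for both programs, the retained contrast lies between 1 - c and 1 - c/2. If ratings in fact refer to the end of each period and residual effect is short, the loss may be nil.

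The implant-site part is secondary. It understates first-period improvement from baseline and adds noise, but it biases the arm contrast only if the sequences are unequal or subjects drop out after period 1. On the NRS assumptions above, the typical bias from chance imbalance is under a tenth of a point. No comparable figure can be given for the pain map.

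The point is worth settling before enrolment, because a look-back window cannot be imposed on ratings already given.

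**What to change.** 1. In Sections 9.1.5 and 9.1.6 and in the case report forms, define the end-of-arm NRS and pain map as referring to the last 24 hours on that program.
2. Have subjects record implant-site pain separately, and leave it out of the target-pain NRS and the map area.
3. In Section 11, analyse the arm contrast within subject with a period term. This deals with the period effect; it complements the scoring window and does not replace it.
4. State that the rating ticked after implant in the Synopsis and Section 4.1 tables is not the period-1 outcome, or reconcile those tables with Section 9.1.1.
5. The sponsor must reconcile the three-day text with the day 4 and day 7 (+/-2) windows, because the 24-hour window helps only when each period is longer than the residual effect plus 24 hours. No particular timing is proposed here.

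Items 1, 2 and 4 cost only form and instruction wording, and item 3 a short analysis paragraph. The small downside is that a 24-hour score varies somewhat more than a three-day summary.
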